**Protocol Title:** 14-1213: 3T MR Angiography of the Hepatic Vasculature

**NCT#:** NCT02299934

**Document Date:** May 28, 2014

- *PI name and contact information:*

Name: [name], MS  
Assistant Professor, Chief  
Division of Abdominal Imaging, Department of Radiology  
University of Colorado School of Medicine  
Address: [name]  
[name]  
[name]  
[name]  
Office: [name]  
[contact]  
e-mail: [contact]

- *Other key personnel:* [name]

- *Project title:* **3T MR Angiography of the Hepatic Vasculature: A pilot comparison study of new non-contrast techniques to post-contrast technique and CT angiography in liver donors.**

- *Project period:* 6 months from the opening of fund

- *Summary and Relevance:*

Currently, all potential liver donors are evaluated with both computed tomography (CT) for the evaluation of hepatic vasculature and magnetic resonance (MR) including MR pancreato-cholangiography (MRCP) for the evaluation of biliary tree anatomy. CT involves the risk of radiation, allergic reactions to contrast, and contrast induced nephropathy. The final goal of this study is to eliminate CT from the pre-transplantation evaluation of potential liver donors by performing the evaluation of hepatic vasculature on MRI.

We propose to evaluate the utility of two new noncontrast MR angiography (MRA) techniques, which do not involve ionizing radiation or exposure to contrast; Inhance 3D Velocity and Inhance Inflow IR. These techniques are available in the GE Signa HDXT 3T MR scanner (General Electric Healthcare, Milwaukee, WI). The Inhance 3D Velocity sequence is based on volumetric 3D phase contrast acquisition with parallel imaging, and the Inhance Inflow IR sequence, on 3D FIESTA (1). These new techniques have shown improved image resolution for imaging renal arteries. However, these techniques have not been evaluated for the hepatic vasculature.

We will recruit 10 potential liver donors who are scheduled for living liver donor CT angiography (CTA) and liver MR. We will obtain CTA and postcontrast MRA images of the hepatic vasculature as standards of care and additional Inhance 3D Velocity and Inhance Inflow IR noncontrast MRA images for study purposes. We will compare these two novel noncontrast MRA techniques to postcontrast MRA and CTA. We will analyze acquisition time, agreement of measurements of diameter among modalities, evaluate visibility of anatomic variations qualitatively and relative signal intensity of the hepatic vasculature quantitatively.

We expect that noncontrast MRA images are comparable to CTA and postcontrast MRA for the pre-transplantation evaluation of the hepatic vasculature. The four techniques will produce similar detection of the normal anatomic structures and potentially important anatomic variations. This result can provide an evidence for the removal of CTA from the current pre-transplantation evaluation process.

This is a pilot study, designed to obtain pilot data for a further, larger, confirmatory study.

- *Hypothesis and Specific Aims:*

Potential liver donors are currently evaluated with both CT including CTA for the evaluation of hepatic vasculature and MR including conventional liver MR and MRCP for the evaluation of biliary tree anatomy. CT evaluation of the potential liver donor requires intravenous iodine contrast administration and at least four-phase CT scanning. If the liver and its vasculature are well evaluated with conventional liver MR and MRA, CT including CTA may be removed from the pre-transplantation evaluation process. Elimination of CT from the pre-transplantation evaluation will remove radiation exposure to healthy candidates and unnecessary CT contrast injection, by which potential allergic reactions or contrast induced nephropathy can be avoided. To satisfy this requirement, MRA should be comparable to CTA in image quality and we will test the following hypotheses regarding CTA, postcontrast MRA, and two new noncontrast MRA techniques.

We will test no difference between the four modalities for the following outcomes:

- #1. A Likert scale for the visibility of hepatic arterial anatomic variations to the level of left and right hepatic arteries as shown on the maximum intensity projection (MIP) images.
- #2. Detection rates of accessory or replaced left or right hepatic arteries, major branch of the middle hepatic vein draining the right lobe, or accessory inferior right hepatic vein(s).
- #3. Correct classification rate of major anatomic variation in portal vein branching pattern.
- #4. Measurements of the diameter and length of the hepatic arteries, portal veins and hepatic veins, including
  - a. The proper, right, middle, and left hepatic arteries.
  - b. The right portal vein at the branching point from the main portal vein.
  - c. The main portal vein diameter 1 cm distal to the bifurcation.
  - d. The right, middle, and left hepatic veins.
  - e. The major branch of the middle hepatic vein draining the right lobe at the insertion to the middle hepatic vein main stem.
  - f. The accessory inferior right hepatic vein at the insertion into the inferior vena cava.
- #5. A Likert scale which rates the examination for how badly the artifacts prevented evaluation by the reader.
- #6. The percentage of examinations with the presence of significant artifacts interfering interpretation.
- #7. The relative signal intensity of the hepatic vasculature on noncontrast and postcontrast MRA.
- #8. Acquisition time.
- #9. The percentage of examinations that caused adverse events, including contrast reactions or claustrophobia.

- *Background and Detailed Research Plan*

Potential living liver donor candidates have been evaluated for the liver and its vasculature and biliary anatomy, mostly by use of CT and CTA, which requires intravenous contrast administration and at least four phase CT scanning including CT cholangiogram. Recently, the intravenous agent for CT cholangiogram has become withdrawn from the market and unavailable. Instead, the biliary anatomy is being evaluated with MR cholangiopancreatography (MRCP). Given the ability of evaluating hepatic parenchyma and characterizing focal hepatic lesions better, MR examinations are usually performed with dynamic liver MR and MRCP protocols prior to and following the administration of intravenous gadolinium contrast. Thus, the candidates are currently being evaluated by CT, CTA, MR and MRCP, which requires high cost and at least two sessions of examinations.

If the liver and its vasculature can be well evaluated with MR and MRA, CT and CTA

may be removed from the pre-transplantation evaluation process. Elimination of CT from the pre-transplantation evaluation will remove radiation exposure to healthy candidates and unnecessary CT contrast injection, by which radiation hazard and potential allergic reactions or contrast induced nephropathy can be avoided. Since MR is considered better than CT for the evaluation of hepatic parenchyma and the characterization of focal hepatic lesions and can also evaluate the upper abdomen for incidental abnormalities, MR can replace CT for the evaluation of the liver and the characterization of focal hepatic lesions. If MRA can evaluate the hepatic vasculature comparably to CTA, thus, MRA can replace CTA and potential living liver donors can be completely evaluated by use of a single modality, MR, by performing conventional liver MR, MRA, and MRCP. Therefore, the purpose of this study is to test MRA sequences for their comparability to CTA in the preoperative evaluation of potential living liver donors.

MRA sequences can be performed with or without intravenous contrast material. Postcontrast MRA sequences are not applicable to patients with poor renal function due to the fear of nephrogenic systemic fibrosis. Noncontrast MRA sequences can be applied regardless of patient's renal function, but have had poor image quality and resolution. However, two new Inhance sequences recently designed by GE Healthcare, including Inhance 3D Velocity and Inhance Inflow IR, provide high-resolution images of the vasculature with short acquisition time and excellent vessel detail (1).

Inhance 3D Velocity is designed to acquire angiographic images in brain and renal arteries with excellent background suppression in a short scan time. By combining a volumetric 3D phase contrast acquisition with parallel imaging, efficient k-space sampling, and pulse sequence optimization, Inhance 3D Velocity is faster than previous generations. Background suppression is improved the optimized pulse sequence design, resulting in better visualization of small branches (1).

Inhance Inflow IR is an angiographic method developed to image renal arteries with the ability to suppress static background tissue and venous flow. Inhance Inflow IR combines the benefits of the inflow effects of time-of-flight (TOF) MRA and the bright luminal signal of the FESTA sequence. This sequence based on 3D FESTA improves SNR while producing bright blood images. A relative inversion pulse is applied over the region of interest, which inverts arterial, venous and static tissue. At the null point of the venous blood, an excitation pulse is applied to generate a signal. The net result is an angiographic image with excellent background suppression and virtually no venous contamination. Uniform fat suppression is achieved using a spectrally selective chemical saturation (SPECIAL) technique (1,2). Both techniques have respiratory gating compatibility (1,2).

Although the arteries of interest by non-contrast MRA in the abdomen were mostly renal arteries, the investigators have started to apply non-contrast MRA techniques to the hepatic arteries (3-6). To our knowledge, however, these improved techniques of Inhance sequences on 3T MR scanners are not yet evaluated for the hepatic vasculature. This pilot study will enable us to optimize these improved non-contrast MRA techniques for the evaluation of the hepatic vasculature and, if successful, will provide us with the benefit of performing pre-transplantation evaluation with MR only, avoiding CT contrast injection and radiation exposure and decreasing cost in potential living liver donors. Hopefully the study will advance to the evaluation of hepatic transplant anastomosis studies later. In our daily practice, there is also a substantial clinical need for detailed angiographic examinations of the hepatic vasculature, without injection of intravenous contrast materials such as in recipients with poor renal function post-transplant.

If the subjects fulfill the criteria for living liver donation and are evaluated for the procedure with CT and MR, they will be included in this study. We will recruit 10 potential living liver donors who had CT and CTA for the evaluation of the liver and hepatic vasculature and will undergo MR and MRCP. Contraindication for MR contrast material is a cause for exclusion from the study. Two healthy volunteers will be examined with MR to optimize the inversion time (TI) and other MRA parameters for the best evaluation

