Data for this study will be entered into a REDCap database, which uses a MySQL database via a secure web interface with data checks used during data entry to ensure data quality. REDCap is a free, secure, web-based application designed to support data capture for research studies. The system was developed by a multi-institutional consortium initiated at Vanderbilt University (7).

- *Statistical analysis plan:*

**Power and Sample Size:** The study will recruit 10 study participants. The study is designed to estimate parameters for a detailed power analysis for a further, larger, confirmatory study.

With 10 participants, the half width for the 95% confidence interval for the proportion of examinations with artifacts will be no more than 0.31.

We describe the analysis plan for Hypothesis #4. The other analysis plans are exactly parallel.

We will fit a general linear multivariate model with doubly repeated measures. The three within participant factors are imaging modality, location (hepatic vein, hepatic artery, and portal vein) and reader. The four imaging modalities are Inhance 3D Velocity noncontrast MRA, Inhance Inflow IR noncontrast MRA, postcontrast MRA, and CTA. The eleven locations of measurement are: The proper, right, middle, left hepatic artery, the right portal vein at the branching point from the main portal vein, the main portal vein 1 cm distal to the bifurcation, the right, middle, left hepatic veins, the major branch of the middle hepatic vein draining the right lobe at the insertion to the middle hepatic vein main stem, the accessory hepatic vein at the insertion into the inferior vena cava. We will average across the readers. We will use an alpha-spending approach to assure an overall 0.05 level for the experiment. At the 0.04 level, we will use a Hotelling-Lawley test to assess the null hypothesis of no modality effect on any of the 11 locations of measurement. If there is a difference, we will conduct two step-down tests to assess the difference between Inhance 3D Velocity non-contrast MRA and CTA, and the difference between Inhance Inflow IR non-contrast MRA and CTA. Finally, we will assess the difference between post-contrast MRA and Inhance 3D Velocity noncontrast MRA, the difference between post-contrast MRA and Inhance Inflow IR non-contrast MRA and the difference between post-contrast MRA and CTA.

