We will examine jackknifed studentized residuals for the presence of outliers and strongly influential observations, using Cook's D to evaluate the significance of the outliers. We will conduct testing for multivariate normality. We will report p-values, parameter estimates, 95% confidence intervals, and produce graphs showing the relationship between the modalities.

We will use the parameter estimates to conduct a power and sample size analysis for a second, larger, confirmatory study, designed to show the non-inferiority of the new modalities to both post-contrast MRA, and CTA.

- *Detailed Budget and Justification:*

Two noncontrast MRA techniques for three vascular structures including hepatic artery, portal vein, and hepatic veins will add 6 sequences and 30 minute to MRI time.

\$283.10 per patient for the additional MRI time (30 minutes) x 12 (2 optimization MRA scans and 10 subjects) = \$3,397.20.

Research assistant: [name]. One 50% full time employed (FTE) research assistant who will work on the entire project during the 6 months. She is needed to help with participant appointment scheduling and do all the evaluation part of the donors and will be the one of the five readers, as she is a qualified radiologist. She will be responsible for researching as well as recording and managing the data, including measures, scores, files and health records. She will assist in ongoing literature review, document review for project, qualitative and quantitative data entry and management, data analysis and checking. She will be responsible for preparing the paper and presentation of the preliminary results for journals, meetings.

1 research assistant at 50% FTE salary for 6 months;  $\$35,200 \times 0.5 \times (6/12) = \$8,800$  for 6 months.

Total amount:  $\$3,397.20 + \$8,800 = \$12,197.20$

- *Journals to which we plan to submit the study:*

Journals in which we wish to publish the results include: Radiology, Journal of Magnetic Resonance Imaging (JMRI), American Journal of Roentgenology (AJR), Hepatology and Journal of Hepatology.

- *Meetings at which we plan to present the study:*

Academic meetings at which we wish to present the results include: The International Society for Magnetic Resonance in Medicine (ISMRM), Radiological Society of North America (RSNA), The American Roentgen Ray Society (ARRS), Society of Abdominal Radiology (SAR), and American Society of Transplant Surgeons (ASTS).

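### The purpose is comparability with CTA, but the formal inference is a gated test of no difference in 10 donors; a non-significant result says little about comparability and should not be offered as support for removing CTA

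*Combined protocol and SAP*

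**What the plan says.** - **Purpose** (Background and Detailed Research Plan): "the purpose of this study is to test MRA sequences for their comparability to CTA in the preoperative evaluation of potential living liver donors".
- **Expected result** (Summary and Relevance): "The four techniques will produce similar detection of the normal anatomic structures and potentially important anatomic variations". The next sentence reads: "This result can provide an evidence for the removal of CTA from the current pre-transplantation evaluation process". The text then calls the study a pilot that gathers data for a larger confirmatory study.
- **Hypotheses** (Hypothesis and Specific Aims): "We will test no difference between the four modalities for the following outcomes", followed by nine outcomes.
- **Size and precision** (Statistical analysis plan): "The study will recruit 10 study participants". The only precision figure is a 95% interval half-width of at most 0.31 for the proportion of examinations with artifacts.
- **Testing** (Statistical analysis plan): "We will use an alpha-spending approach to assure an overall 0.05 level for the experiment". Readings are averaged over readers, and a Hotelling-Lawley test at 0.04 addresses a modality effect on 11 measurement sites. Then: "If there is a difference, we will conduct two step-down tests to assess the difference between Inhance 3D Velocity non-contrast MRA and CTA", with a matching test for Inhance Inflow IR. The plan is written for diameters and lengths (#4) and is said to carry over to the other outcomes.
- **Reporting and next step** (Statistical analysis plan): p-values, estimates, 95% confidence intervals and graphs across modalities are promised. The estimates will then be used to size a second study, "designed to show the non-inferiority of the new modalities to both post-contrast MRA, and CTA".

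Neither part of the document gives a margin, an agreement limit or a tolerable number of missed variants. The Summary lists agreement of diameters among the analyses, but the analysis plan names no method for it.

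**The concern.** A test of no difference can give evidence that modalities differ. When it fails to reject, that alone is not evidence that they are alike, and the smaller and noisier the study, the more often it fails to reject. Here the hoped-for result is similarity, and the Summary links that result to dropping CTA from the work-up of healthy donors.

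The order of testing adds to the difficulty. The two contrasts that bear most directly on CTA, each noncontrast technique against CTA, are formally tested only after the global test has found a difference. In the scenario that the investigators expect, neither contrast is tested, and the plan does not say that its estimate and interval will still be shown. A reader of the report could then be left with a non-significant global p-value and the Summary's sentence about CTA, without the figures needed to judge how large a discrepancy remains possible.

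**Working it through.** **Inputs from the documents.** n = 10 donors, each imaged with all four modalities (paired data); overall level 0.05 and 0.04 for the global test, sidedness not stated; stated half-width 0.31. The documents give no SD of paired differences, variant prevalence, discordance rate or margin. Effects below are therefore in units of the SD of the paired difference (after any averaging over readers), and the prevalences are assumptions.

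**The plan's own figure.** 1.96 × √(0.5 × 0.5 / 10) = 0.3099, so 0.31 reproduces. It describes the precision of one proportion, not of a difference between modalities.

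**Why the plan's own test is not used.** Four modalities give 3 contrasts at each of 11 sites, so 3 × 11 = 33 response contrasts against 10 − 1 = 9 error degrees of freedom. With an unstructured covariance the Hotelling-Lawley statistic cannot be computed. That is a separate matter. It means that the figures below use simpler paired analyses to show what 10 donors can tell.

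**Diameters, single-site paired t test.** Noncentral t with 9 df and noncentrality d × √10, where d is the true bias in SD units:

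| True bias d | Power, two-sided 0.04 | Power, two-sided 0.05 |
|---|---|---|
| 0.5 | 26% | 29% |
| 0.8 | 57% | 62% |
| 1.0 | 77% | 80% |

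At 0.05, a bias of 0.5 SD is therefore missed 100 − 29 = 71% of the time. At 0.04, 80% power needs a bias of about 1.04 SD.

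95% interval half-width for a paired mean difference: t(0.975; 9) / √10 = 2.262 / 3.162 = 0.72 SD. An observed difference of exactly zero would still be compatible with a bias of up to 0.72 SD in either direction.

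**Detection, exact McNemar test, one reading per donor.** Suppose that MRA misses a variant in k donors in whom CTA shows it, and that the reverse never occurs. Then p = 2 × 0.5^k:
- k = 5: p = 0.0625
- k = 6: p = 0.031

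So misses alone reach p < 0.05 only if at least 6 of the 10 donors carry the variant and at least 6 are missed. The chance of 6 or more carriers is a ceiling on the chance of a significant result from misses alone:

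| Assumed carriage | 20% | 30% | 40% | 50% | 60% |
|---|---|---|---|---|---|
| P(6 or more of 10) | 0.6% | 4.7% | 17% | 38% | 63% |

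The upper end matters because outcome #2 lists several variants, and pooled carriage per donor may exceed 40%.

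**No misses at all.** The upper limit of the exact two-sided 95% interval with 0 misses in m carriers is 1 − 0.025^(1/m). That is 31% for m = 10, 60% for m = 4 and 84% for m = 2.

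**What a non-inferiority claim on a paired mean would need.** At one-sided 0.025, 80% power and a true difference of zero, the normal formula ((1.960 + 0.842) / margin)² gives 32 donors for a margin of 0.5 SD and 88 for 0.3 SD. With the t correction these become 34 and 90. With 10 donors the power is 29% and 13%. These margins are illustrations only.

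**The case against.** The strongest case on the other side is that this is an openly labelled pilot.

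- **No decision rule.** A reader might infer that the plan treats a non-significant test as proof of comparability. It does not say so. The Summary's sentence refers to an expected similarity of detection, is hedged, and stands in the rationale. The analysis plan has no rule on CTA. This stands.
- **Estimates are planned.** A reader might infer that noncontrast MRA is never compared with CTA if the global test does not reject. Only the step-down tests are conditional. The promise of estimates and 95% intervals is not tied to the global test. This stands in part: the plan does not say which contrasts get intervals, or how agreement of diameters will be assessed.
- **Non-inferiority comes later.** Preliminary evidence followed by a confirmatory study is a coherent sequence, so this is not a failed confirmatory design. That is fair, but it is also why the sentence on removing CTA asks too much of this study.
- **The power figures are not the plan's.** McNemar and single-site t tests are substitutes, and the prevalences are assumed. This stands. The figures show how little 10 paired observations can exclude, not the operating characteristics of the planned test.
- **No practice changes on this result.** Participants have CTA as standard of care, and the follow-up plan points to further work and funding. A reader might infer direct harm to donors, which the documents do not support. The risk lies in how the result is later cited.

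**Conclusion.** The concern holds as a mismatch between the stated purpose and the formal inference, made worse by one over-reaching sentence and an underspecified reporting plan. Comparability is the aim, the tests are of no difference, the noncontrast-versus-CTA tests are gated on a significant global result, and nothing in the documents defines comparable.

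The size of the problem is that 10 donors leave room for large discrepancies behind a non-significant result: power of 26% at 0.04 (29% at 0.05) for a bias of 0.5 SD, an interval half-width of 0.72 SD, and p = 0.0625 with five one-way misses. The McNemar p-values depend only on the number of one-way discordant donors. The t figures assume roughly normal paired differences and are in SD units because no SD is given. The carriage figures rest on assumed prevalences.

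The change is worth making because it alters what the study can properly conclude and costs almost nothing.

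**What to change.** 1. **Summary and Relevance.** Qualify the sentence on removing CTA, for example: *A non-significant difference will not be taken as evidence of comparability; this pilot estimates differences between modalities to plan the confirmatory non-inferiority study.*
2. **Statistical analysis plan, diameters and lengths (#4).** State that each noncontrast-minus-CTA paired difference will be reported with its 95% interval whether or not the global test rejects, and name limits of agreement as the method for diameters.
3. **Statistical analysis plan, detection and classification (#2 and #3).** Report per-donor cross-tables of each noncontrast technique against CTA, showing the cells where one shows the finding and the other does not.
4. **Confirmatory study.** The sponsor should set and justify the non-inferiority margin there. Fixing one in this pilot is debatable, since intervals of this width would seldom settle the question.

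The cost is some rewording and a few more intervals and tables, with no extra donors, scans or readings. The limits of agreement will be imprecise with 10 donors and should be described so. The real downside is that the pilot can no longer claim by itself to support removing CTA.

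### Outcome #2's detection rate has no stated denominator or reference, so similar rates would not show that MRA and CTA find the same variants in the same donors

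*Combined protocol and SAP*

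**What the plan says.** Under Hypothesis and Specific Aims, outcome #2 reads "Detection rates of accessory or replaced left or right hepatic arteries, major branch of the middle hepatic vein draining the right lobe", and the list ends with the accessory inferior right hepatic vein. The sentence that introduces the outcomes says "We will test no difference between the four modalities for the following outcomes". No denominator is given, and no reference is named. Outcome #3, by contrast, is "Correct classification rate of major anatomic variation in portal vein branching pattern"; it speaks of correctness, although it does not name a reference either.

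Background and Detailed Research Plan sets entry as "If the subjects fulfill the criteria for living liver donation and are evaluated for the procedure with CT and MR, they will be included" and adds "We will recruit 10 potential living liver donors who had CT and CTA". Neither statement selects on variant status. Five readers each read all four examinations of every donor and assign the branching patterns to categories. CTA is one of the four examinations compared and is not designated as truth.

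The Statistical analysis plan sets out one analysis, for #4: average over the five readers, then test for a modality effect. For the rest it says "The other analysis plans are exactly parallel". On size it says "The study will recruit 10 study participants", and it intends the estimates to be used to size a later non-inferiority study.

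Summary and Relevance plans agreement for diameters only. It expects the four techniques to detect variants similarly and concludes "This result can provide an evidence for the removal of CTA from the current pre-transplantation evaluation process".

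**The concern.** The question that matters for replacing CTA is whether MRA shows, in a given donor, the variant that CTA shows in that donor. A comparison of the share of donors called positive by each modality answers a different question. A positive call in a donor without the variant raises that share by exactly as much as a miss in a carrier lowers it. A technique that misses a replaced artery in one donor and reports one in another donor has the same rate as CTA.

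Two uses of the result are at stake. The protocol would take similar detection as support for dropping CTA, and a marginal rate cannot carry that inference. The confirmatory study also needs planning values for detection and false calls, and the analysis as prespecified reports neither.

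**Working it through.** **Inputs.** From the protocol and SAP: 10 donors, five readers, four modalities, and a global test at the 0.04 level. The documents give no variant prevalence, so carrier counts and prevalences below are assumptions. CTA is treated as correct for illustration only.

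**1. The plan's own figure.** The only design figure is a 95% half-width of at most 0.31 for the proportion of examinations with artifacts. It reproduces: 1.96 × √(0.25/10) = 0.3099. No figure is given for outcome #2.

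**2. What can be computed as written.** Score each donor 1 (called positive) or 0. With M misses and F false calls relative to CTA, the mean paired difference, MRA minus CTA, is (F − M)/10. It is zero exactly when F = M, whatever the size of F and M. The within-donor design does not alter this, because the modality effect is tested on mean differences. Averaging over readers does not alter it either: one reader's miss in one donor can be offset by another reader's false call in a different donor.

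**3. Examples with 10 donors.**

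| Carriers | Missed | False calls | CTA rate | MRA rate | Sensitivity | False-positive rate | Agreement | Kappa |
|---|---|---|---|---|---|---|---|---|
| 2 | 2 | 2 | 2/10 | 2/10 | 0/2 = 0% | 2/8 = 25% | 60% | −0.25 |
| 3 | 1 | 1 | 3/10 | 3/10 | 2/3 = 67% | 1/7 = 14% | 80% | 0.52 |
| 3 | 2 | 2 | 3/10 | 3/10 | 1/3 = 33% | 2/7 = 29% | 60% | 0.05 |
| 4 | 2 | 2 | 4/10 | 4/10 | 2/4 = 50% | 2/6 = 33% | 60% | 0.17 |
| 3 | 3 | 0 | 3/10 | 0/10 | 0/3 = 0% | 0/7 = 0% | 70% | 0.00 |

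Kappa for the third row: observed agreement 0.60, chance agreement 0.3 × 0.3 + 0.7 × 0.7 = 0.58, so (0.60 − 0.58)/(1 − 0.58) = 0.05. The last row is a technique that only misses; its rate does fall.

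**4. In expectation.** With prevalence p, the positive-call rate is p·Se + (1 − p)(1 − Sp). It equals p when p(1 − Se) = (1 − p)(1 − Sp). For Se = 0.5 this needs Sp = 0.875, 0.786 or 0.667 at p = 0.2, 0.3 or 0.4. Expected per-donor agreement is then 80%, 70% or 60%.

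**5. What a test at n = 10 would show.** The exact McNemar test serves here as a simple stand-in for the planned multivariate test. In the three settings of step 4 it gives p < 0.05 in about 0.02%, 0.13% and 0.44% of simulated trials (200,000 replicates). Without any offsetting, missing 3 of 3 variants gives p = 2 × 0.5³ = 0.25. Six discordant donors, all in one direction, are needed for p = 2 × 0.5⁶ = 0.031; five give 0.062.

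**6. Whether carriers will be present.** The chance that none of 10 donors carries a variant is (1 − p)¹⁰: 35%, 11% or 3% at p = 0.1, 0.2 or 0.3.

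**7. Precision within carriers.** If all k carriers are detected, the exact 95% lower limit for sensitivity is 0.025^(1/k): 0.16, 0.29 or 0.40 for k = 2, 3 or 4.

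**The case against.** The strongest reply is that the all-donor denominator is inferred. A detection rate can mean the share of existing variants that are found, and on that reading nothing offsets. This stands as a comment on the wording. It does not remove the defect: that rate needs a reference and a count of carriers, the protocol supplies neither for #2, and false calls would still go unreported.

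A reader might infer that errors cancel whenever carriers and non-carriers are both enrolled, or that a poor technique will match CTA's rate. The documents do not support either inference. Offsetting needs both kinds of error, and a zero difference needs equal numbers. Nothing in the protocol says that false calls would be as common as misses; it describes older noncontrast MRA as poor in quality and resolution, which could lead mainly to misses.

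Nor do the documents show that every listed variant will be present in some donors and absent in others. A variant may have no carriers. If every donor has the middle hepatic vein branch, which is one of the eleven measurement sites, its all-donor rate is its sensitivity.

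Two further replies are partly right. At n = 10 a non-significant difference is likely even without offsetting, so reading non-significance as similarity is a problem in its own right. And no data are lost, because per-donor calls are recorded on every examination; what is missing is the prespecified analysis. That this is a pilot limits the consequence, but its estimates are meant to feed the next study.

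**Conclusion.** The point holds in a limited form. As written, outcome #2 can be computed only as a marginal positive-call rate, and similar marginal rates do not establish that MRA and CTA identify the same variants in the same donor. With an assumed 3 carriers, rates can be identical while per-donor agreement is 60% and kappa 0.05. How far this happens depends on the number of carriers and on the balance of misses and false calls, and the documents fix neither. The conclusion that follows in every case is that the planned analysis reports neither sensitivity nor false-positive rate, and that the step from similar detection to dropping CTA is not supported by this outcome. It is related to the unnamed reference in #3 but is not the same point: naming a reference for #3 would leave #2 a rate over all donors. The change should be made before the readings are analysed.

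**What to change.** For each variant separately, and for each of the three MRA techniques, prespecify a paired per-donor 2x2 table against the same donor's CTA. Report detection among CTA-positive donors, positive calls among CTA-negative donors, and overall agreement, with exact intervals. Keep the arterial variants, the middle hepatic vein branch and the accessory inferior right hepatic vein apart, and state the number of CTA-positive donors for each, including zero.

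State in advance how five readers' CTA calls become one comparator, for example the majority reading, with same-reader pairs as a sensitivity analysis. Describe variants seen only on MRA as discordant with CTA, not as proven false, since the protocol does not establish CTA as truth. State that a non-significant difference in rates will not be read as similarity.

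The cost is SAP wording and a few tables from calls already collected. The downsides are very wide intervals (a lower limit of 0.29 even if 3 of 3 carriers are detected) and that CTA becomes the comparator for this outcome, so the tables cannot show MRA doing better than CTA.
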